# 3.2. Study Design - R/R Cohort

The R/R Cohort will be evaluated in 3 stages. As of Amendment 3, in the first stage, 10 patients (the R/R Safety Cohort) have been treated in a safety run-in to evaluate the safety profile of magrolimab monotherapy in this R/R population. Based on aggregate clinical, safety, PK, and pharmacodynamic data in the R/R Safety Cohort, the CTSC will determine whether enrollment may begin in an Expansion stage of the initial R/R Cohort, in which a total of up to 36 additional patients in the R/R Expansion Cohort will be treated to evaluate the clinical activity of magrolimab in combination with azacitidine. In the R/R Expansion Cohort, magrolimab will be administered 1 mg/kg twice weekly for Cycle 1 Week 1 (Day 1 and Day 4); 15 mg/kg on Cycle 1 Day 8, 30 mg/kg on Cycle 1 Day 11 and Day 15, 30 mg/kg weekly on Cycle 1 Day 22 through end of Cycle 2, and 30 mg/kg Q2W starting Cycle 3 and thereafter, as shown in Table 3-1, based on clinical, PK, and pharmacodynamic data and for evaluation of a more convenient dosing regimen. If a patient has only received Day 1 treatment for a cycle, the patient may transfer to the Q2W dosing regimen with that cycle, for the balance of the cycle and beyond, even if they were previously receiving magrolimab QW at Cycle 3 and beyond.

If an increased dose or frequency of dosing is explored, additional cohorts will use a standard 3+3 design. Based on emerging clinical data, the CTSC may expand this cohort beyond the initial 36 patients for further safety, efficacy, and/or dosing data. In addition, individual patients may be transitioned from a magrolimab Q2W to Q4W dosing regimen by the Investigator with approval from the Medical Monitor. As of Amendment 6, up to 23 R/R MDS patients may be enrolled in an additional R/R MDS Magrolimab Monotherapy cohort. Patients will be enrolled in this cohort in a Simon's 2-stage design. With a 1-sided significance level of 0.05 and 80% power, the null hypothesis that the magrolimab monotherapy ORR is 9% will be tested against the alternative of 30%. In the first stage, 11 patients will be enrolled. If there are 1 or fewer responses observed in these 11 patients, the cohort will be stopped. Otherwise, 12 additional patients will be accrued, for a total of 23. This cohort was stopped after 11 patients enrolled per CTSC decision in October 2020. The null hypothesis will be rejected if 5 or more responses are observed in 23 patients. R/R MDS patients who do not achieve an objective response after the first protocol response assessment may have azacitidine added to magrolimab for subsequent cycles. For patients who respond to magrolimab monotherapy and then progress, azacitidine may be added to magrolimab and patients can still be continued to be treated with the combination.

The Schedule of Assessments tables for the R/R Expansion Cohort and the R/R MDS Magrolimab Monotherapy Cohort are provided in Section 7.1. The Schedule of Assessments table for the R/R Safety Cohort, which is now closed, is provided in Appendix F.

Table 3-1. Dose and Schedule for R/R AML/MDS Cohorts

		Dose Schedule (Day per 28-day Cycle)		
Cohort	Drug/Dose/Route	Cycle 1	Cycle 2	Cycle 3+
R/R AML/MDS	Magrolimab - 1 mg/kg IV	Day 1, 4	_	_
(Safety Cohort)	Magrolimab - 15 mg/kg IV	Day 8		
	Magrolimab - 30 mg/kg IV	Day 11, 15, 22	Day 1, 8, 15, 22	Day 1, 8, 15, 22
R/R AML/MDS	Magrolimab - 1 mg/kg IV	Day 1, 4	_	_
(Expansion Cohort) a	Magrolimab - 15 mg/kg IV	Day 8	_	_
	Magrolimab - 30 mg/kg IV	Day 11, 15, 22	Day 1, 8, 15, 22	Day 1 and 15
	Azacitidine - 75 mg/m² SC or IV b	Day 1-7	Day 1-7	Day 1-7
R/R MDS (Magrolimab Monotherapy Cohort) a,c	Magrolimab - 1 mg/kg IV	Day 1, 4	_	_
	Magrolimab - 15 mg/kg IV	Day 8	_	_
	Magrolimab - 30 mg/kg IV	Day 11, 15, 22	Day 1, 8, 15, 22	Day 1 and 15

Abbreviations: AML = acute myeloid leukemia; CTSC = Clinical Trial Steering Committee; IV = intravenous; MDS = myelodysplastic syndrome; Q2 = every 2; R/R = Relapsed/Refractory; SC = subcutaneous; UK = United Kingdom; US = United States.

- a. The magrolimab maintenance dose in R/R Expansion and R/R MDS Monotherapy will be changed to Q2 weeks beginning at Cycle 3.
- b. Azacitidine administered per region-specific labeling: SC in UK or US; IV in US only.
- c. R/R MDS patients who do not have an objective response with magrolimab at the first protocol response assessment may have azacitidine added to magrolimab for subsequent cycles. The azacitidine dosing schedule given is identical to that of the R/R AML/MDS expansion cohort. For patients who respond to magrolimab monotherapy and then progress, azacitidine may be added to magrolimab and patients can still be continued to be treated with the combination.

# 3.3. Study Design - Treatment-naïve/Unfit (TN/U) Cohort

## 3.3.1. TN/U Cohort Dose Levels

All patients in the TN/U Cohort will receive magrolimab in combination with azacitidine. Magrolimab will be administered twice weekly through Cycle 1 Day 11; weekly beginning Cycle 1 Day 15 through end of Cycle 2; and then 30 mg/kg either weekly (for the TN/U Dose Evaluation Cohort) or Q2W (for the TN/U Expansion Cohort) starting Cycle 3 and thereafter, as shown in Table 3-2. This dose regimen was selected based on emerging clinical, PK, and pharmacodynamic data. Because dosing changed from twice weekly to weekly (beginning Week 3 of Cycle 1 and thereafter) with the previous Amendment 3, patients who are being treated under a previous Amendment may transition to the new (weekly) dosing schedule at the next cycle, or as determined by the Investigator. If a patient has only received Day 1 treatment for a cycle, the patient may transfer to the Q2W dosing regimen for the balance of the cycle and beyond. As of Amendment 6, a TP53 mutant TN/U AML subcohort was added to the TN/U Expansion Cohort. This TP53 mutant TN/U AML subcohort will have magrolimab administered on a Q2W dosing regimen starting Cycle 3 and thereafter (see Table 3-2). In addition, Amendment 6 reflects the CTSC decision to transition all TN/U Expansion Cohort patients (both existing and new) to a magrolimab dose of 30 mg/kg Q2W starting Cycle 3 and beyond.

Azacitidine will be administered according to region-specific drug labeling, either SC or IV, at the standard dose of 75 mg/m^2 on Days 1 to 7 of each 28-day cycle for both dose levels. Magrolimab will be given at least 1 hour after the azacitidine infusion/injection is completed.

Dose evaluation of magrolimab will begin with the designated dose level shown in Table 3-2. Decisions related to potential dose escalation or de-escalation will be based on the first 4 weeks of treatment in the current cohort, referred to as the "Dose-Limiting Toxicity (DLT) Assessment Period," in conjunction with ongoing assessments for patients on prior cohorts who continued therapy beyond 4 weeks. Decisions regarding additional cohorts to further refine the MTD or recommended Phase 2 dose and

schedule (RP2DS) will be made by the CTSC. The CTSC may create additional dose cohorts to be evaluated using a 3+3 design including, but not limited to, adding additional dose cohorts, adding intermediate dose steps (e.g., an additional intrapatient dose escalation step), reducing intermediate dose steps (e.g., removal of an intrapatient dose escalation step), or exploring a dose schedule of weekly or up to Q4W, if supported by emerging PK and clinical data. In addition, individual patients may be transitioned to a magrolimab Q2W to Q4W dosing regimen by the Investigator with approval from the Medical Monitor.

It should be noted that treatment with azacitidine as monotherapy is recommended for a minimum of 6 cycles (refer to the azacitidine prescribing information). All patients without evidence of treatment failure, relapse after CR or CRi, or unacceptable toxicity should continue study treatment for at least 6 cycles. Patients may be discontinued from the treatment per Investigator's discretion prior to reaching the recommended minimum cycles for any of these reasons detailed in Section 8.1.

The Schedules of Assessments for the TN/U Dose Evaluation Cohort and the TN/U Expansion Cohort are provided in Section 7.1.

Table 3-2. Dose Level and Schedule for TN/U AML/MDS Cohorts (Including TP53 Mutant AML)

			nedule (Day per 28	(Day per 28-day Cycle)	
Cohort/Dose Level	Drug/Dose/Route	Cycle 1	Cycle 2	Cycle 3+	
TN/U Dose Evaluation Cohort: Level 1 b	Magrolimab - 1 mg/kg IV	Day 1, 4	_	_	
	Magrolimab - 15 mg/kg IV	Day 8			
	Magrolimab - 30 mg/kg IV	Day 11, 15, 22	Day 1, 8, 15, 22	Day 1, 8, 15, 22	
	Azacitidine - 75 mg/m² SC or IVª	Days 1-7	Days 1-7	Days 1-7	
TN/U Expansion Cohort (including TP53 mutant AML subcohort): 30 mg/kg IV b	Magrolimab - 1 mg/kg IV	Day 1, 4	_	_	
	Magrolimab - 15 mg/kg IV	Day 8			
	Magrolimab - 30 mg/kg IV	Day 11, 15, 22	Day 1, 8, 15, 22	Day 1, 15	
	Azacitidine - 75 mg/m² SC or IVª	Days 1-7	Days 1-7	Days 1-7	

Abbreviations: AML = acute myeloid leukemia; IV = intravenous; MDS = myelodysplastic syndrome; R/R = Relapsed/Refractory; SC = subcutaneous; TN/U = Treatment-naïve/Unfit; UK = United Kingdom; US = United States.

## 3.3.2. TN/U Cohort Dose Evaluation

Dose evaluation will follow a 3+3 dose evaluation design. Up to 6 evaluable patients may be enrolled in each dose cohort. If none or 1 of the first 3 patients experiences a DLT, the cohort will be expanded to 6 patients. If 2 or more patients experience DLTs, the MTD dose level will have been exceeded, enrollment to that cohort will halt. CTSC will determine whether to treat additional patients at lower or higher dose levels or evaluate alternative dose regimens. The MTD for the TN/U Cohort is the maximum dose level at which at least 6 patients are treated with magrolimab and azacitidine and less than 34% of these patients experience a DLT. The RP2DS will be determined by the CTSC (Section 11.6) based on review of all available safety, efficacy, and PK data.

a. Azacitidine administered per region-specific labeling: SC in UK or US; IV in US only.

b. As of Amendment 6, all existing and newly enrolled TN/U cohort patients are to follow 30 mg/kg Q2W magrolimab dosing starting Cycle 3 and beyond.

Dose escalation/de-escalation and cohort expansion decisions will be reviewed and approved by the CTSC. Dose escalation or de-escalation may occur at dose increments or decrements, respectively, of up to 50% of the maximum prior dose as determined by the CTSC. The CTSC may add additional patients to any dose level to collect additional safety and PK information.

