# 3.3.3. TN/U Cohort Dose-limiting Toxicity Evaluation

Dose evaluation decisions will be made by the CTSC based on the first 4 weeks of treatment for each patient, referred to as the "Dose-limiting Toxicity (DLT) Assessment Period." The first patient in each 3+3 dose evaluation cohort must complete at least 2 weeks of treatment before additional patients may be enrolled in the cohort. Subsequent patients may be enrolled simultaneously. The third patient in a cohort must complete the DLT Assessment Period prior to enrolling the next 3 patients at the same dose level. A new patient may be enrolled whenever a patient becomes nonevaluable for DLT. The CTSC may decide whether a fourth patient can be enrolled to the same cohort prior to the first 3 patients completing the DLT Assessment Period, in order to have an extra patient in case that 1 of the 3 earlier patients are not evaluable for DLT or if there is a DLT within the cohort requiring cohort expansion.

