## 3.3.4. TN/U Cohort Definition of DLT-evaluable Patients

Patients in the TN/U Dose Evaluation cohort are considered evaluable for assessment of DLT if EITHER of the following criteria are met during the DLT Assessment Period:

- The patient experienced a DLT at any time after initiation of the first infusion/injection of magrolimab.
- The patient completed at least 4 infusions of magrolimab and 4 infusions/injections of azacitidine.

For the TN/U Dose Evaluation cohort, patients who withdraw before completing the 4-week DLT Assessment Period for reasons other than a DLT, or who do not fulfill either of the criteria above, will not be evaluable for assessment of DLT for dose review decisions and will be replaced in the cohort.

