# 3.4. Study Design - RBC Transfusion-dependent Low-risk MDS Cohort

The RBC Transfusion-dependent Low-risk MDS Cohort consists of a safety run-in phase and an expansion phase. In the safety run-in phase, 6 patients will be enrolled and will receive magrolimab monotherapy, with a safety evaluation after all 6 patients complete at least Cycle 2 Day 15 treatment. For this cohort, after the first patient is enrolled, subsequent patients in this initial 6-patient group can be enrolled simultaneously 1 week later. This safety evaluation is being conducted given that a 60 mg/kg dose of magrolimab will be administered starting in Cycle 2, of which this highest dose has not yet been tested in MDS patients. However an equivalent dose of 60 mg/kg given in 1 week (30 mg/kg twice weekly) has already been administered to MDS and AML patients in this trial and has been well tolerated. If 1 or fewer DLTs are observed in these 6 patients, then expansion may proceed.

If the DLT rate is ≥ 33% in at least 6 patients enrolled, then dose de-escalation to a lower magrolimab dosing regimen (i.e., 45 mg/kg Q4 weekly or alternative) can be explored as determined by the CTSC in an additional cohort of 6 patients with subsequent expansion. Patients may have their magrolimab dose interval changed (i.e., to more frequent [Q2W] or less frequent [> Q4W]) at any time on therapy based on CTSC recommendations or Sponsor requirement.

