# 3.4.1. RBC Transfusion-dependent Low-risk MDS Cohort Definition of Dose-limiting Toxicity

DLT definitions for the RBC Transfusion-dependent Low-risk MDS Cohort are similar to those for the TN/U Safety Evaluation Cohort and are defined in Section 3.3.5 with the exception that the DLT period is through the first 6 weeks (Cycle 2 Day 15). If the DLT rate is ≥ 33% in at least 6 patients enrolled, then the 60 mg/kg magrolimab dose would be considered to have exceeded the MTD. In this case, the CTSC may decide to proceed with expansion at a magrolimab dose regimen of 30 mg/kg QW for Cycle 2 followed by Q2W from Cycle 3 onward or explore a dose de-escalation to a lower magrolimab dosing regimen. The CTSC may decide to enroll additional patients in the safety run-in to further evaluate safety of the magrolimab 60 mg/kg dosing regimen or a lower dosing regimen. Patients may have their magrolimab dose interval changed (i.e., to more frequent [Q2W] or less frequent [> Q4W]) at any time on therapy based on CTSC recommendations or Sponsor requirement.

An efficacy assessment for the first 6 patients will be assessed at Cycle 3 Day 1. For patients who do not respond to magrolimab monotherapy, azacitidine can be subsequently added for continuation of therapy according to the dose schedule in Table 7-3. After the 6 patients have completed their post-Cycle 2 efficacy assessment, the CTSC will determine based on safety and efficacy data whether further expansion to 14 additional patients will occur with magrolimab monotherapy or magrolimab in combination with azacitidine. Expansion of these 14 patients can be simultaneously enrolled. Based on emerging safety, PK/PD, and/or efficacy data, the CTSC may expand this cohort to additional patients beyond the 20 total with either magrolimab monotherapy or in combination with azacitidine.

Table 3-3. Dose Level and Schedule for RBC Transfusion-dependent Low-risk MDS Cohort

Cohort/Dose	Dose Schedule (Day per 28-day Cycle			-day Cycle)
Level	Drug/Dose/Route	Cycle 1	Cycle 2	Cycle 3+
Safety Run-in	Magrolimab - 1 mg/kg IV	Day 1	<del></del>	_
(Magrolimab 60 mg/kg)	Magrolimab - 30 mg/kg IV	Day 8, 15, 22	<del></del>	_
·	Magrolimab - 60 mg/kg IV	_	Day 1	Day 1
	Azacitidine - 75 mg/m² SC or IVª	_	<del>_</del>	Days 1-5
Expansion	Magrolimab - 1 mg/kg IV	Day 1		_
	Magrolimab - 30 mg/kg IV	Day 8, 15, 22	<del></del>	_
	Magrolimab - 60 mg/kg IV d	_	Day 1	Day 1

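### Section 3.3.2 contradicts itself at 2 DLTs in 6 patients: the halt sentence says the MTD is exceeded, while the MTD definition (less than 34%) accepts 33.3%

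*Protocol*

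**What the plan says.** Section 3.3.2 describes a 3+3 evaluation. On cohort size it says: "Up to 6 evaluable patients may be enrolled in each dose cohort". On expansion: "If none or 1 of the first 3 patients experiences a DLT, the cohort will be expanded to 6 patients". The halt sentence follows at once: "If 2 or more patients experience DLTs, the MTD dose level will have been exceeded", and enrollment to that cohort then stops. It does not say out of how many patients.

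The paragraph goes on to define the MTD as the highest dose level at which "at least 6 patients are treated with magrolimab and azacitidine and less than 34% of these patients experience a DLT". The section closes by letting the Clinical Trial Steering Committee (CTSC) add patients to any dose level, so a dose can have more than 6.

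Two neighbouring sections bear on the denominator and the order of entry. Section 3.3.3 has the third patient finish the DLT period "prior to enrolling the next 3 patients at the same dose level". Section 3.3.4 says that patients who do not qualify "will not be evaluable for assessment of DLT for dose review decisions and will be replaced in the cohort".

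The low-risk MDS cohort has its own rule, and it is consistent. Section 3.4 says: "If 1 or fewer DLTs are observed in these 6 patients, then expansion may proceed". Section 3.4.1 states the consequence for the observed DLT proportion as follows: "≥ 33% in at least 6 patients enrolled, then the 60 mg/kg magrolimab dose would be considered to have exceeded the MTD". There, 2 of 6 exceeds the MTD.

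**The concern.** A dose-decision rule should give one answer for each possible DLT count. Here one count in a full cohort of the planned size gets two. Two careful readers with the same data, 2 DLTs in 6 patients, could reach opposite conclusions about the dose, and each could point to a sentence in the same paragraph.

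This is not detail deferred to a statistical analysis plan. The rule is fixed in the protocol, and it is the pre-specified check on the CTSC, which is chaired by a sponsor representative (Section 11.5) and also performs the data monitoring functions (Section 11.6).

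There is also a smaller wording point. The MTD sentence counts treated patients, while the cohort is sized in evaluable patients and Section 3.3.4 bases dose decisions on evaluable patients. In a cohort with replacements the two denominators can differ.

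**Working it through.** The plan states no operating characteristic for this rule, so there is no figure to reproduce. The check has three steps.

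**1. Both sentences at the planned size, n = 6 (Section 3.3.2)**

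| DLTs | Rate | Halt sentence (2 or more = exceeded) | MTD definition (less than 34%) |
|---|---|---|---|
| 0 | 0% | acceptable | acceptable |
| 1 | 16.7% | acceptable | acceptable |
| 2 | 33.3% | **exceeded** | **acceptable** |
| 3 or more | 50% or more | exceeded | exceeded |

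At 6 patients, exactly 2 DLTs is the only conflict. The low-risk rule (at least 33% exceeds) rejects 2/6 = 33.3%.

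**2. More than 6 patients at a dose**

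The halt sentence rejects every count of 2 or more, and the definition accepts any rate below 34%. The conflicting counts are:

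- n = 7: 2/7 = 28.6%
- n = 8: 2/8 = 25.0%
- n = 9: 2/9 = 22.2% and 3/9 = 33.3%
- n = 10: 2/10 = 20.0% and 3/10 = 30.0%

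**3. How often the disputed outcome would arise**

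Assume that each patient independently has DLT probability p, that patients enter as 3 and then 3 (Section 3.3.3), and that the cohort expands only after 0 or 1 DLT in the first 3. The protocol gives no value for p; 20%, 33% and 40% are assumptions.

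- If 2 of 6 is too many, the dose is accepted with probability (1−p)^6 + 6p(1−p)^5.
- Exactly 2 of 6 can be reached with 0 DLTs then 2 (1 × 3 = 3 arrangements) or 1 then 1 (3 × 3 = 9 arrangements). The probability is 12p²(1−p)^4.
- If 2 of 6 is allowed, the acceptance probability is the sum of the two.

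At p = 0.20: 0.2621 + 0.3932 = 0.655; disputed 12 × 0.04 × 0.4096 = 0.197; sum 0.852.

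| Assumed p | Accepted, at most 1 of 6 | Accepted, at most 2 of 6 | Disputed (exactly 2 of 6) |
|---|---|---|---|
| 20% | 65.5% | 85.2% | 19.7% |
| 33% | 35.8% | 62.1% | 26.3% |
| 40% | 23.3% | 48.2% | 24.9% |

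**The case against.** The strongest reply is that the halt sentence was meant for the first 3 patients only. It follows directly on a sentence about 0 or 1 DLT in the first 3, and 2 or more is the exact complement. Halting enrollment matters mainly before the cohort is full. And at 6 patients a cut-off of 34% rather than 33% changes one outcome only, 2 of 6, so it may have been chosen to admit it. This reading is coherent and may be what was intended. But the words limiting the rule to the first 3 appear in the preceding sentence and are absent from this one, and the sentence declares the MTD exceeded as well as stopping entry. On the narrow reading, Section 3.3.2 would also have no explicit stopping count for the expanded cohort; it would have to be inferred from the MTD definition.

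The low-risk rule does not settle the TN/U intent either way. It governs a different population, a 6-patient monotherapy run-in and a 6-week DLT period. It shows only that the same protocol decides 2 of 6 against the dose elsewhere.

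It is also fair that neither sentence fixes the dose mechanically. The CTSC approves escalation, de-escalation and expansion, and selects the recommended dose on all safety, efficacy and PK data. The percentages above therefore describe a rule applied as written. They are not probabilities that this trial erred.

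The objection that live impact is small stands in full. The Dose Evaluation Cohort closed with 8 patients enrolled (Section 11.4). Tables 7-1 to 7-3 mark the R/R Expansion, TN/U Expansion and low-risk schedules as closed to enrollment, and Appendix F archives the rest.

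**Conclusion.** The inconsistency is real but minor. As written, Section 3.3.2 both rejects and accepts a dose with 2 DLTs in 6 patients, and it does the same at further counts if more than 6 are treated. No other TN/U text resolves it. Under the assumed DLT rates of 20% to 40%, the disputed result at 6 patients would arise in roughly 20% to 26% of cohorts, given independent patients and entry in two groups of 3.

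A reader might infer that the dose carried forward was wrongly chosen. The documents do not support that: nothing shows that 2 DLTs occurred in the Dose Evaluation Cohort.

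A reader might also infer that the statement in Section 1.2.2.1, that no MTD was reached at 30 mg/kg weekly, depends on which sentence was applied. That does not follow either. Section 1.2.2.1 gives no DLT count, it summarises 36 combination-treated patients rather than the Dose Evaluation Cohort alone, and at 6 patients the two sentences differ only at exactly 2 DLTs.

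What remains is any further 3+3 cohort. Section 3.3.1 still lets the CTSC create them. Section 3.2 provides for a standard 3+3 design in R/R patients without saying whether Section 3.3.2 governs it.

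**What to change.** Amend the halt sentence and the MTD definition together, with DLT-evaluable patients as defined in Section 3.3.4 as the denominator in both. Changing only the definition is not enough: an unchanged halt sentence would still conflict at 2 of 7 or 2 of 8.

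- **If 2 of 6 is unacceptable** (as in Sections 3.4 and 3.4.1): *If 2 or more of up to 6 evaluable patients (or 33% or more if more than 6 are evaluable) experience a DLT, the MTD has been exceeded.* Define the MTD as the highest dose with at least 6 evaluable patients and less than 33% with a DLT.
- **If 2 of 6 was meant to be acceptable**: keep 34% in the definition and write *If 2 or more of the first 3 evaluable patients, or 34% or more of 6 or more evaluable patients, experience a DLT, the MTD has been exceeded.*

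Apply the chosen rule to any further 3+3 cohort opened under Section 3.3.1, and state whether it also governs Section 3.2. The closed cohort need not be re-decided. The cost is a short wording change in Section 3.3.2 at the next amendment, with a line in Section 3.2 on whether the rule applies there. No new data are needed.
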